2. STUDY OBJECTIVES

To evaluate the efficacy and safety of 15 mg of DU-176b in patients with NVAF aged 80 years or older who are ineligible for available oral anticoagulants (warfarin, dabigatran, rivaroxaban, apixaban, or edoxaban) at the approved dosage.** To evaluate the superiority of 15 mg of DU-176b compared to placebo in a composite endpoint of stroke and SEE as the primary efficacy endpoint.

^{§:} INR controlled at between 1.6 and 2.6 with warfarin

^{**:} For warfarin, INR controlled at between 1.6 and 2.6

3. STUDY DESIGN

[figure not shown]
The efficacy and safety of 15 mg of DU-176b once daily will be evaluated in a randomized, double-blind, placebo-controlled, parallel-group, multicenter, event-driven study in patients with NVAF aged 80 years or older who are ineligible for available oral anticoagulants (warfarin, dabigatran, rivaroxaban, apixaban, or edoxaban) at the approved dosage.**

The workflow from informed consent to the final follow-up examination is shown in Figure 3-1.

The investigator or subinvestigator will obtain consent from potential subjects for this study and then enter their subject information into interactive response technology (IRT). Within 30 days after informed consent, an eligibility assessment examination will be performed to determine whether or not the subjects meet all inclusion criteria and exclusion criteria, and the eligibility assessment results for the subjects will be entered into IRT. Subject enrolled in IRT will be assigned randomly to the DU-176b group or placebo group in a 1:1 ratio.

After randomization, study treatment will be started on the same date that notification of study drug identifiers is given. Completion of the study will be declared when the planned number of subjects with primary efficacy endpoint events (stroke and SEE) has been collected. Administration of the study drug will be continued until the examination at completion of study treatment performed within 60 days after the declaration of completion of the study. When the investigator or subinvestigator requires to know the study treatment assignment for each subject to determine the subsequent treatment after the final administration of the study drug, the study treatment can be continued until the final follow-up examination after obtaining consent from the subject. The final follow-up examination will be performed in the subjects, in principle, within a month after notifying their study treatment assignments.

Figure 3-1 Study Design

- a: Subjects who provided consent will continue to receive the study treatment. The planned duration of the additional study treatment is 3 to 4 months.
- b: Completion of the study will be declared when the planned number of subjects with primary efficacy endpoint events has been collected.
- c: For subjects who do not continue the study treatment, the final follow-up examination will be performed within 30 to 37 days after the examination at completion of study treatment. For subjects who continue the study treatment, the final follow-up examination will be performed, in principle, within a month after notifying their study treatment assignments.

<Rationale>

The objective of administering oral anticoagulant therapy to patients with NVAF is to reduce the risk of thromboembolisms such as stroke or SEE, and clinical studies of anticoagulant therapy in patients with NVAF generally use the occurrence of stroke and SEE as efficacy endpoints. To assess the incidence of clinical events such as these, it is necessary to collect a certain number of subjects with efficacy events, and therefore this study will be conducted as an event-driven study. As there is no specification about the period for which it is necessary to reduce the risk of thromboembolism in patients with NVAF, the duration of study treatment for each subject will not be specified, and instead the study treatment will be continued until the visit directly after completion of the study is declared, when the required number of efficacy events have been collected.

The study subjects are patients with NVAF with a high risk of stroke but who have not received oral anticoagulants (non-VKA oral anticoagulants or warfarin) due to concerns about bleeding, or who are receiving warfarin at an anticoagulant strength not

recommended in the guidelines.^{††} For this reason, it is not possible to use warfarin or non-VKA oral anticoagulants at the approved dosage^{‡‡} as a control. Antiplatelet drugs are also unsuitable as the control in this study, since they are not the standard of care for reducing the risk of stroke in patients with AF, and antiplatelet therapy in patients with AF is not recommended. Thus, as it is not feasible to select a specific medication as a control drug, we have decided to use a placebo as a control to evaluate the efficacy and safety of administration of 15 mg of DU-176b once daily. To minimize subject selection bias, we have decided to conduct randomization after the eligibility of subjects has been determined, and to minimize treatment bias and assessment bias, we have selected double-blinding as the blinding level. The clinical events selected as efficacy and safety endpoints will be assessed under blinded conditions by event assessment committees independent of the investigators and Sponsor.

^{††:} INR controlled at below 1.6

^{‡‡:} For warfarin, INR controlled at between 1.6 and 2.6

4. STUDY POPULATION

4.1 Selection of Subjects

Subjects who meet all of the following inclusion criteria and exclusion criteria, and provide written consent of their own free will, will be selected. In the case of patients with concurrent dementia who are unable to provide written consent in person, written approved consent from a legally acceptable representative will be mandatory (see "15.3 Informed Consent").

4.1.1 Inclusion Criteria

- 1) Patients with NVAF with history of AF documented by any electrical tracing within the 1 year prior to the day of informed consent
- Patients with at least 2 of the following thromboembolism risk factors (CHADS₂ index score ≥ 2)
 - i) Congestive heart failure
 - ii) Hypertension
 - iii) Age ≥ 75 years
 - iv) Diabetes mellitus
 - v) History of transient ischemic attack (TIA) or cerebral infarction (excluding occurrences within the 30 days prior to the day of randomization)
- 3) Patients with aged \geq 80 years on the day of informed consent
- 4) Patients who are ineligible for available oral anticoagulants (warfarin, dabigatran, rivaroxaban, apixaban, or edoxaban) at the approved dosage,*** and with at least 1 of the following bleeding risks:
 - i) Severe renal impairment (creatinine clearance [CLcr] calculated by the Cockcroft-Gault formula ≥ 15 mL/min and < 30 mL/min)
 - ii) History of bleeding from critical area or organ (such as intracranial, intraocular, or gastrointestinal bleeding)
 - iii) Low body weight ($\leq 45 \text{ kg}$)
 - iv) Continuous use of acidic non-steroidal anti-inflammatory drugs (NSAIDs)
 - v) Patients using 1 antiplatelet drug (for a purpose other than prophylaxis of

Subjects such as those not eligible for continued administration at the approved dosage for the drug due to concerns about bleeding risk, or those who have not been administered available oral anticoagulants at the approved dosage but are expected to have a high bleeding risk from available oral anticoagulants at the approved dosage.

^{***:} For warfarin, INR controlled at between 1.6 and 2.6

cardioembolic stroke)

<Rationale>

The study subjects are elderly patients with NVAF aged ≥ 80 years who are ineligible for oral anticoagulants (warfarin, dabigatran, rivaroxaban, apixaban, or edoxaban) at the approved dosage.*** The study will enroll the patients with NVAF diagnosed by their physician to be ineligible to receive treatment with available oral anticoagulants at the approved dosage after consideration of the bleeding risk from administration of warfarin, and also consideration of bleeding risk in accordance with the precautionary text in the Warnings section of the package inserts for non-VKA oral anticoagulants stating "when using this drug, a careful consideration should be given to whether administration of this drug is appropriate, taking bleeding risk into consideration."

- 1) To ensure that the patient is an AF patient.
- A CHADS₂ index score ≥ 2, at which level all available oral anticoagulants are recommended in the Guidelines for Pharmacotherapy of Atrial Fibrillation, ⁶ was selected.
- 3) Patients with aged ≥ 80 years⁸⁾ were selected, since patients of this age account for at least half of the patients with NVAF for whom anticoagulant therapy is recommended but who do not receive anticoagulants despite being at particularly high risk from stroke.
- 4) Renal impairment, low body weight, and concomitant administration of antiplatelet drugs are considered to be factors related to the occurrence of major bleeding during anticoagulant therapy. ⁶⁾ Bleeding such as intracranial, intraocular, intrathecal, retroperitoneal, or intraarticular bleeding, or a history of bleeding from critical areas or organs such as gastrointestinal tract bleeding ¹⁹, ²⁰, ²¹ or concomitant administration of acidic NSAIDs²² are considered to be factors for bleeding risk.

4.1.2 Exclusion Criteria

- Transient AF secondary to other reversible disorders (e.g. thyrotoxicosis, cardiac or thoracic surgery, pneumonia, severe anemia)
- 2) Patients who received warfarin, dabigatran, rivaroxaban, apixaban, or edoxaban within the 8 weeks prior to the day of randomization
- 3) Patients receiving warfarin with INR controlled at ≥ 1.6 in 2 of the 3 most recent examinations, including the eligibility assessment examination, measured at least 4 weeks apart (patients with INR ≥ 1.6 at the eligibility assessment examination are

excluded)

- 4) Patients with particularly high bleeding risk meeting any of the following criteria:
 - i) Active bleeding on the day of informed consent*
 - *: Subcutaneous bleeding will be included if there is at least 1 hematoma with a maximal diameter of at least 5 cm, and urinary findings will be included if frank hematuria is observed.
 - ii) Unresolved peptic ulcer on the day of informed consent
 - iii) Hemoglobin < 9 g/dL, or platelet count < $10 \times 10^4/\mu L$ at the eligibility assessment examination
 - iv) Hereditary hemorrhagic disease
- 5) Cerebral infarction or TIA within the 30 days prior to the day of randomization
- 6) Patients with rheumatic valve disease
- History of prosthetic valve replacement (mechanical or biological valves)*
 *: History of mitral valve repair is allowed in the study.
- 8) Patients with infective endocarditis
- 9) Patients with atrial myxoma
- 10) Observed presence of left ventricular or atrial thrombus
- 11) Observed hereditary thrombophilia
- 12) Patients with scheduled electrical or pharmacologic defibrillation between the day of informed consent and the time of the examination at completion of study treatment
- 13) Uncontrolled hypertension (systolic blood pressure persistently > 160 mmHg or diastolic blood pressure persistently > 100 mmHg)
- 14) CLcr calculated by the Cockcroft-Gault formula < 15 mL/min
- 15) Patients who have started hemodialysis or who may start hemodialysis by the time of the examination at completion of study treatment
- 16) Patients receiving dual antiplatelet therapy (e.g., aspirin plus a thienopyridine) at the time of informed consent, or those expected to receive dual antiplatelet therapy after the time of informed consent, who cannot safely discontinue use of either of the antiplatelet drugs
- 17) Patients with hepatic function disorder accompanied by coagulation disorder
- 18) History of acute myocardial infarction (MI) within the 30 days prior to the day of randomization
- 19) Serious heart disease such as cardiac failure with New York Heart Association (NYHA) classification ≥ 3 or unstable angina pectoris
- 20) Patients who currently have malignancy. Patients diagnosed with malignancy within the 2 years prior to the day of informed consent, or who have received

treatment with cancer therapy (drugs, radiation, and/or surgery) within the 2 years prior to the day of informed consent, except for patients with adequately treated basal cell carcinoma of the skin, resected squamous cell carcinoma of the skin, and cervix carcinoma in situ.

- 21) History of receiving any other study drugs within the 60 days prior to the day of informed consent
- 22) Patients the investigator or subinvestigator considers ineligible

<Rationale>

- 1 to 3) To select eligible subjects for this study.
- 4) Due to the possibility of an increased risk of major bleeding from the study treatment.
- 5 to 11) Due to the markedly high risk of thromboembolism.
- 12 to 22) To ensure the safety of subjects and to conduct this study appropriately.

4.1.3 Subject Enrollment

4.1.3.1 Workflow of Subject Enrollment

Subjects will be enrolled in the study using IRT, including IWRS, using the Internet. The enrollment procedure for subjects is shown in Figure 4.1-1.

Study site

Subject information entered into IRT

Subject identification code assigned
Screening list prepared
Inclusion criteria and exclusion criteria checked

If determined eligible:

Subject enrollment details entered into IRT

Randomization of subjects

Study drug identifiers checked
Study drugs with the specified study drug identifier administered

Figure 4.1-1 Enrollment Procedure for Subjects

After obtaining written informed consent from the subjects (or legally acceptable representatives), the investigator or subinvestigator will assign subject identification codes and prepare a subject screening list, and assess the eligibility of subjects, within

30 days.

The investigator or subinvestigator will enter the required items for all subjects from whom consent has been obtained (including consent from legally acceptable representatives) into IRT. The IRT will assign study-specific subject numbers.

Next, the investigator or subinvestigator will enter the eligibility assessment results for the subjects into IRT. The day of enrollment is defined as the date entered into IRT as the date when eligibility was determined. The day of withdrawal is defined as the date entered into IRT as the date when ineligibility was determined. IRT will perform randomization on the enrolled subjects and assign them study drug identifiers. The investigator or subinvestigator will confirm the study drug identifiers displayed in IRT and then administer the study drugs marked with those study drug identifiers, on the same date notification of study drug identifiers is given.

If the investigator or subinvestigator determined that a subject is ineligible, the investigator or subinvestigator will explain the reason for this to the subject (or legally acceptable representative) and administer regular treatment. If there are any subjects from whom consent was obtained but who were determined ineligible, the investigator or subinvestigator will enter the fact that these subjects are ineligible in the subject screening list. If the investigator or subinvestigator later determines that a subject is eligible for this study, the investigator or subinvestigator will obtain written consent from the subject (or legally acceptable representative) again, and enroll the subject according to the procedure specified in this section.

4.1.3.2 If Notification Is Received That the Subject Is Receiving Treatment from Another Physician

The investigator or subinvestigator will find out whether or not subjects from whom consent was received are receiving treatment from another physician (another department at the study site or another medical institution). If a subject is receiving treatment from another physician, the investigator or subinvestigator will notify the other physician that the subject is participating in the clinical study, with the consent of the subject (or legally acceptable representative). The fact that this notification has been given will be recorded, for example in medical records.

4.2 Individual Subject Interruption or Discontinuation of Study Drug, Individual Subject Discontinuation of Study Participation, and Termination of the Entire Study

4.2.1 Study Drug Interruption

4.2.1.1 Interruption and Resumption of Study Drug

If systolic blood pressure persistently exceeds 160 mmHg or diastolic blood pressure persistently exceeds 100 mmHg on the same day, study treatment for the relevant subject will be promptly interrupted. After treatment is temporarily interrupted, repeat measurements will be made at least one week apart, and if it is found that the above conditions are not met, the study treatment will be resumed.

The study treatment may be temporarily interrupted at the discretion of the investigator or subinvestigator, for example due to the occurrence of an adverse event or invasive treatment or tests being performed. Except in emergencies, surgery or invasive treatment or tests will be performed when at least 24 hours have passed since study treatment. To determine whether or not study treatment can be resumed before the examination at completion of study treatment, the investigator or subinvestigator will assess the subject's clinical state within the 7 days after the study drug interruption, and at least every 8 weeks thereafter. If the investigator or subinvestigator determines that the study treatment can be resumed, and the subject (or legally acceptable representative) consents to this, the study treatment will be resumed, and the study procedures at the specified visit directly after resumption will also be resumed. If the study treatment has not been resumed at the time of the examination at completion of study treatment, it will be considered that study treatment has been discontinued at this point.

If the study treatment is interrupted, the investigator or subinvestigator will enter the duration of study drug interruption, the reason for interruption, and whether or not the study treatment can be resumed on the case report form. If the study treatment is interrupted due to an adverse event, the investigator or subinvestigator will enter information on the case report form in accordance with "9.4 Adverse Event Information to Be Reported" and "9.6 Action When an Adverse Event Occurs."

4.2.1.2 Follow-up Survey During Study Drug Interruption

The investigator or subinvestigator will survey the following items until the examination at completion of study treatment or until the resumption of treatment at the visit specified in "6. STUDY PROCEDURES" at least every 8 weeks at a visit or by telephone, and will enter the information on the case report form. If the subject cannot be contacted by

telephone, surveys will be performed by letter.

- 1) Whether any serious adverse events have occurred
- 2) Whether any efficacy events have occurred
- 3) Whether any bleeding events have occurred
- 4) Whether any of the following drugs (including over-the-counter drugs) have been used: anticoagulants, thrombolytic drugs, antiplatelet drugs, intravenous antiarrhythmic drugs, or acidic NSAIDs
- 5) Blood pressure and pulse rate (only if the subject makes a visit)
- 6) Laboratory tests determined to be appropriate by the investigator or subinvestigator (only if the subject makes a visit). However, if warfarin is being administered, measurement of PT-INR is mandatory.

4.2.2 Study Drug Discontinuation

4.2.2.1 Study Drug Discontinuation Criteria

If a subject meets any of the following criteria, the investigator or subinvestigator will promptly discontinue the study treatment of the relevant subject, and take suitable action in response. As far as possible, the investigator or subinvestigator will perform the examination at discontinuation and make every attempt to ensure the safety of the subject, and will enter the reason for discontinuation on the case report form.

- 1) If hemodialysis is started
- 2) If the subject refuses to receive the study drug, or the legally acceptable representative refuses to allow the subject to receive the study drug, based on a request made of his/her own free will (if consent is given for the follow-up survey specified in "4.2.2.2 Follow-up Survey After Study Drug Discontinuation" after study drug discontinuation, the follow-up survey will be performed)
- 3) If the study treatment is interrupted and is not resumed by the time of the examination at completion of study treatment
- 4) If the investigator or subinvestigator determines that the study treatment should be discontinued for any other reason

In the case of subjects who meet criterion 2) above (withdrawal of consent for the study treatment), if consent to resume the study treatment at the free will of the subject (or legally acceptable representative) is obtained before the examination at completion of study treatment, and the investigator or subinvestigator considers that there are no problems with the subject's clinical state, the study treatment may be resumed. If the

study treatment is resumed, the study procedures at the specified visit directly after resumption will be performed.

4.2.2.2 Follow-up Survey After Study Drug Discontinuation

The investigator or subinvestigator will survey the following items until the examination at completion of study treatment at least every 8 weeks at a visit or by telephone, and will enter the information on the case report form. If the subject cannot be contacted by telephone, surveys will be performed by letter. In the case of subject meeting "4.2.2.1-2) Study Drug Discontinuation Criteria" (withdrawal of consent for the study treatment), the investigator or subinvestigator will also find out whether the subject (or legally acceptable representative) is willing to resume the study treatment, and will enter the results on the case report form.

- 1) Whether any serious adverse events have occurred
- 2) Whether any efficacy events have occurred
- 3) Whether any bleeding events have occurred
- 4) Whether any of the following drugs (including over-the-counter drugs) have been used: anticoagulants, thrombolytic drugs, antiplatelet drugs, intravenous antiarrhythmic drugs, or acidic NSAIDs
- 5) Blood pressure and pulse rate (only if the subject makes a visit)
- 6) Laboratory tests determined to be appropriate by the investigator or subinvestigator (only if the subject makes a visit). However, if warfarin is being administered, measurement of PT-INR is mandatory.

4.2.3 Discontinuation of Study Participation and Termination of the Entire Study 4.2.3.1 Discontinuation of Study Participation Due to Withdrawal by Subject

If a subject (or legally acceptable representative) makes a request to withdraw not only from receiving the study drug but also from participation in the study, including all study procedures or follow-up survey related to the study, the investigator or subinvestigator will promptly withdraw the relevant subject from the study and take the suitable action for the subject in response. The investigator or subinvestigator will also perform the examination at discontinuation and make every attempt to ensure the safety of the subject as far as the subject (or legally acceptable representative) is willing to cooperate, and will enter the date of discontinuation and the reason for discontinuation on the case report form.

4.2.3.2 Discontinuation of Study Participation in the Event of a Major Protocol Deviation

In the event of a major deviation (a situation where it is not feasible to continue the study safely) relating to a subject, the investigator or subinvestigator will promptly withdraw the relevant subject from the study and take the suitable action for the subject in response. The investigator or subinvestigator will perform follow-up survey of abnormal findings at the time of discontinuation, and as far as the subject (or legally acceptable representative) is willing to cooperate, will perform the examination at discontinuation and make every attempt to ensure the safety of the subject, and will enter the date of discontinuation and the reason for discontinuation on the case report form.

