	Eligibility assessment		weeks	weeks from	Examination at	Final follow-up
	examination		from	Week 48	completion of study	examination ^b
	exami	паноп	Week 4 to	onward	treatment ^a /examination	examination*
			Week 48	onward	at discontinuation	
Visit	0	1	2-13	14-		
Visit window					Within the 60 days	*****************
					after declaration of	Within the 30 to
	Within		± 14		completion of the	37 days after
	days p		daysc	± 14 days ^c	study ^c	examination at
	random	ization ^c	,		Within the 7 days after	completion of
					discontination	study treatment ^c
Informed consent	X					
IRT entry (entry of						
subject information)	X					
Baseline subject		l				
	← X	$\zeta \rightarrow$				
characteristics ^d		I				
IRT entry (entry of		17				
eligibility assessment		X				
result), randomization						- f
Study drug administration		←			• 4	· > ¹
Study drug compliance		←			—	
Height	← 3	$\zeta \rightarrow$				
Physical						
examination/medical	← 2	$\prec \rightarrow$	X	X	X	X
interview						
Body weight	← 2	X →	X	X	X	X
Blood pressure/pulse rate	← ∑	K →	X	X	X	X
Hematology testg	← 2	K →	Xh	X	X	X
Blood chemistry testg	← 2		Xh	X	X	X
Endocrinology testg	←2		Xh	X	X	X
Urinalysisg	← 2	 	Xh	X	X	X
CLeri	←2		Xh	X	X	X
12-lead ECG	←2		X ^j	X ^k	X	X
Head CT or MRI ¹	←2		A.	Λ	Λ	Λ
Whether surgery or	← 2					
		←				
hospitalization occurred		4				m
Adverse events						
Efficacy/bleeding events		←				
Concomitant medication	-				—	
Follow-up survey after						
interruption/discontinuati			ı ←			
on of study drug ⁿ						
Pharmacokinetic blood						
samplingg						
Blood sampling for			X°			
pharmacodynamic		X				
indicatorsg						
Blood sampling for		х	X°			
biomarker measurementg		Λ	A.			
PGx banking ^p			← :	$X^q \rightarrow$		
	_	_	_	_		

a: Will not be performed on subjects withdrawn from the study.

b: Will be performed in subjects who continue the study treatment, in principle, within a month after notifying their study treatment assignments.

c: Will be calculated by taking the date of the scheduled visit to be Day 0.

d: Falling score, frailty assessment, and one-leg standing test with eyes open will be surveyed by the

time of Visit 3.

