6. STUDY PROCEDURES

6.1 Study Procedure and Specimen Collection Schedule

The timing of study procedures and specimen collection in this study is shown in Table 6-1. The investigator or subinvestigator will record information such as the results of study procedures, the dates and times of specimen collection, the state of specimens at the time of sampling, and comments about these.

The examination at completion of study treatment will be performed within 60 days after the declaration of completion of the study, including subjects for whom study treatment has been interrupted or discontinued. Completion of the study will be declared when the planned number of subjects with primary efficacy endpoint events (stroke and SEE) has been collected.

The final follow-up examination will be performed within the 30 to 37 days after the examination at completion of study treatment. For subjects who continue the study treatment after the examination at completion of study treatment, the final follow-up examination will be performed, in principle, within a month after notifying their study treatment assignments.

Follow-up survey of subjects for whom study treatment has been interrupted or discontinued will be performed according to "4.2.1.2 Follow-up Survey During Study Drug Interruption" and "4.2.2.2 Follow-up Survey After Study Drug Discontinuation" respectively.

Surveys of subjects for whom "4.2.3 Discontinuation of Study Participation and Termination of the Entire Study" applies will be deemed complete as of the examination at discontinuation, which will be performed as far as is possible.

Table 6-1 Study Procedure and Specimen Collection Schedule

		_	D	uration of study	traatmant	
	P1:-11	:1:6				
	Eligibility assessment examination		Every 4	Every 8 weeks from	Examination at	Final fall
			weeks from Week 4 to	Week 48	completion of study	Final follow-up examination ^b
	examir	lation			treatment ^a /examination at	examination
TT-14		1	Week 48	onward	,	
Visit	0	1	2–13	14-	discontinuation	
Visit window	Within days pr randomi	rior to	±14 days ^c	±14 days ^c	Within the 60 days after declaration of completion of the study ^c Within the 7 days after discontination ^c	Within the 30 to 37 days after the examination at completion of study treatment ^c
Informed consent	X					
IRT entry (entry of subject						
information)	X					
Baseline subject	- X					
characteristics ^d	$\leftarrow X$. →				
IRT entry (entry of						
eligibility assessment		X				

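### Low priority: a subject the investigator withdraws under 4.2.3.2 has no scheduled event survey after the discontinuation examination, even without withdrawing consent to follow-up, and if event-free is censored there in the ITT primary analysis

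*Combined protocol and SAP*

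**What the plan says.** Section 4.2.3.2 begins "In the event of a major deviation (a situation where it is not feasible to continue the study safely) relating to a subject" and continues that "the investigator or subinvestigator will promptly withdraw the relevant subject from the study". The decision is the investigator's. The subject's willingness to cooperate matters only for the discontinuation examination and the safety measures. The one follow-up named is that the investigator "will perform follow-up survey of abnormal findings at the time of discontinuation". Withdrawal at the subject's own wish is a separate rule, section 4.2.3.1, for a subject or representative who "makes a request to withdraw not only from receiving the study drug but also from participation in the study".

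Section 6.1 then says that surveys of subjects for whom section 4.2.3 "applies will be deemed complete as of the examination at discontinuation, which will be performed as far as is possible". For the completion examination, note a to the schedule (synopsis and Table 6-1) reads "Will not be performed on subjects withdrawn from the study". In sections 6.14, 6.15 and 7.1, collection of efficacy and bleeding events closes at the discontinuation examination for subjects withdrawn from participation. Section 11.4.2.1.1 censors event-free subjects on that day.

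Subjects who only stop study drug are treated differently. The criteria in section 4.2.2.1 include the open one "If the investigator or subinvestigator determines that the study treatment should be discontinued for any other reason". Under section 4.2.2.2 the investigator then "will survey the following items until the examination at completion of study treatment at least every 8 weeks at a visit or by telephone", or by letter if the telephone fails. Those who refuse the drug are surveyed if they consent to it.

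**The concern.** Section 11.2.1.1 defines the ITT set as everyone randomized, dosed or not, and section 11.4.2.1.1 counts events regardless of dosing. Outcome collection should therefore stop only when the subject no longer agrees to it or the whole study ends. Section 4.2.3.2 adds a third stopping point, set by the investigator after randomization and for a safety-related reason.

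The Cox model treats a censored subject as having the same later risk as comparable subjects still under follow-up. Someone removed because the study could not safely continue may have a different risk. If removals, or the relative risk after removal, differ between arms, the hazard ratio is biased, in either direction. This applies to the primary endpoint and to the section 7.2 endpoints that include death and major bleeding. Section 11.3.3 rules out imputation, and events that were never collected may not be recoverable later.

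**Working it through.** **Could another provision fill the gap?**
- The follow-up of abnormal findings in 4.2.3.2 concerns findings present at discontinuation. It is not a recurring search for new events.
- Section 9.6.1 follows an existing adverse event, if need be past the observation period.
- Sections 6.13 and 9.6.2 ask in general terms for serious adverse event reporting until the final follow-up examination. That visit is timed from a completion examination that withdrawn subjects do not have, or from notification of the assignment for those continuing drug. A stroke reported this way also falls outside the window in 7.1 and 11.4.2.1.1.
- In 11.4.2.1.2 the on-treatment mITT analysis censors no later than 3 days after the final dose. The PPS (11.2.1.3) may exclude these subjects for a major violation.

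None is a scheduled event survey that counts in the endpoint.

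**The plan's own figure.** From 11.6: hazard ratio 0.5, two-sided 5%, power 80%, 1:1. Schoenfeld events = 4 × (1.960 + 0.842)² / (ln 0.5)² = 65.35, against the stated 65. Power at 65 events is 79.8%. The figure reproduces.

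**Patient-years.** With 400 per arm, uniform 2-year enrolment, 1.5 years of further follow-up, hazard λ and no dropout, patient-years = 400 × [1 − (e^(−1.5λ) − e^(−3.5λ)) / (2λ)] / λ. This gives 937 at λ = 0.05 (placebo) and 968 at λ = 0.025 (edoxaban). I use 900 per arm to allow for some loss. Observed events are then 900 × 0.025 = 22.5 and 900 × 0.05 = 45.

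**Assumptions, none in the documents.** A share p of one arm is removed, each subject loses 1.25 years, and later risk is k = 2 or 3 times that arm's usual rate. Missed events = 400 × p × 1.25 × rate × k. Restored patient-years = 500p. The hazard ratio is approximated by the ratio of rates.

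**At p = 1% (4 subjects in one arm)**

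| Removal | k | Missed events | Hazard ratio if followed |
|---|---|---|---|
| Edoxaban only | 2 | 0.25 | (22.75/905)/0.05 = 0.503 |
| Edoxaban only | 3 | 0.375 | (22.875/905)/0.05 = 0.506 |
| Placebo only | 2 | 0.5 | 0.025/(45.5/905) = 0.497 |
| Placebo only | 3 | 0.75 | 0.025/(45.75/905) = 0.495 |
| Equal p and k in both arms | 2 or 3 | – | 0.500 |

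For scale, p = 10% with k = 3 gives (26.25/950)/0.05 = 0.553 for edoxaban only and 0.025/(52.5/950) = 0.452 for placebo only. That is 40 removals in one arm and none in the other.

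**Could the conclusion change?** The critical hazard ratio at 65 events is exp(−1.96 × 2/√65) = 0.615. From an observed 0.50 with k = 3, solving 0.50 × (900 + 1500p)/(900 + 500p) = 0.615 gives p = 0.234, so more than 20% edoxaban-only removal.

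From an observed 0.60 the answer depends on the event count used. At 900 patient-years per arm there are 27 + 45 = 72 events, and the boundary is exp(−3.92/√72) = 0.630. At 812.5 patient-years there are 65 events, and the boundary is 0.615. Recomputing the boundary with the missed events added, break-even edoxaban-only removal is about 5.4% (k = 3) or 11.8% (k = 2) in the first case, and about 2.4% or 5.2% in the second. With that spread, no single break-even rate should be quoted.

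**The case against.** The best counter-argument is that the rule is a last resort. It applies when the study itself, not just the drug, cannot safely go on for the subject. Anything short of that goes through interruption (4.2.1, including the need for prohibited medication under 5.3.1) or drug discontinuation (4.2.2), where the survey at least every 8 weeks is kept (subject to consent for those who refuse drug). Nothing suggests 4.2.3.2 would be used often, or at all. Section 5.2.2.2 blinds subjects, investigators and sponsor, which makes one-arm removal an extreme case. All of this stands, and it is why the point is low priority.

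A reader might infer more than the documents support:
- That the protocol contradicts itself. It does not: 4.2.3.2, 6.1, note a and 11.4.2.1.1 agree with one another. This is an avoidable design choice.
- That these subjects get no further follow-up. Abnormal findings, existing adverse events and, in general terms, serious adverse events are still covered.
- That the trial loses power. It runs to 65 events, so power is largely protected.
- That the sensitivity analyses are inadequate. Section 11 leaves detailed methods to a Statistical Analysis Plan whose detail is not in the text reviewed, so this cannot be judged. No analysis, however, can use events that were never collected.
- That a handful of removals would overturn the result. That needs a borderline estimate, strongly one-sided removal and raised risk afterwards, all together.

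**Conclusion.** The point holds as a cheap, low-priority improvement. An investigator-initiated withdrawal under 4.2.3.2 ends the scheduled event survey for a subject who may still be willing to be followed, and the ITT primary analysis censors that subject if event-free.

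The likely effect is very small. The movement from 0.50 to between 0.495 and 0.506 rests on an assumed 1% removal confined to one arm, with the assumed time lost and raised risk. The direction cannot be predicted. The documents give no removal frequency, so the true size cannot be determined from them. Confidence in the reading of the text is high; confidence that it would matter in practice is low.

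**What to change.** State in 4.2.3.2, 6.1 and note a (synopsis schedule and Table 6-1) that a subject withdrawn under 4.2.3.2 continues the existing 4.2.2.2 survey, by visit, telephone or letter, to the completion examination, unless the subject or representative withdraws consent to follow-up. Death is captured as an efficacy event under 6.14.

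Align the cut-off for subjects withdrawn from participation in 6.13, 6.14, 6.15, 7, 7.1, 7.2, 9, 9.1, 9.2, 11.4.2.1.1 and 11.4.5, so that it applies only to 4.2.3.1 and 4.2.3.4. Death under 4.2.3.3 is unchanged. Section 9.2 must be included because 9.1 defines bleeding events as a kind of adverse event, and 9.2 ends adverse events at the discontinuation examination for these subjects. Section 6.13 is needed because the 4.2.2.2 survey also collects serious adverse events.

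Count the events found in the ITT analysis, make the primary-analysis change through a 15.7 amendment as 11.5 requires, and report 4.2.3.2 withdrawals by arm. Study-drug and clinical-care decisions stay as they are.

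The cost is a wording amendment across these sections and a few extra contacts per affected subject. The survey and its case report form entry already exist.
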